5.10 Data Collection, Management and Analysis

5.10.1 Data Collection Methods

Each participant will be given a unique trial Participant IDentification number (PID). Data will be collected at the time-points indicated in the Trial Schedule. Assessment scores should be entered into the REDCap database along with copies of each assessment for monitoring purposes. Baseline and follow-up assessments will be paper based and scored in blinded fashion.

The preferred method of data collection is direct online entry of data onto the central database, stored on servers based at NCTU by members of the SIGHT trial team working within each research site. Data may be entered onto paper Case Record Forms (CRFs) prior to entry onto the database, if paper forms are used, they must be transcribed. Staff will receive training on data collection and use of the online system (see Section 4.2).

Data collection, data entry and queries raised by a member of the SIGHT trial team will be conducted in line with the NCTU and trial specific Data Management Standard Operating Procedure.

Identification logs, screening logs and enrolment logs will be kept at the trial site on a secured computer or in a locked cabinet within a secured room if not incorporated in the database.

Participant identifiable data may be stored in the REDCap database to enable participants to be contacted by site staff for the purpose of trial delivery. There will be a clear logical

separation of participant identifiable data from the trial data which is uploaded to REDCap using restricted permissions.

Where there is a requirement for study materials to be stored and/or shared electronically outside of the study database (e.g. supporting materials shared via OneDrive, SharePoint or similar), the mechanism for achieving this will be appropriate in terms of governance, regulatory and legal compliance, and resource to administer it will be identified.

Clinical trial team members will receive trial protocol training. All data will be handled in accordance with the Data Protection Act 2018.

5.10.2 Data Management

Data will be entered under the participants' PID numbers onto the central database stored on servers based at NCTU. Transfer of all MRI and clinic brain imaging data between sites and UEA will be done via Sectra Image Exchange Portal (SIEP), a secure cloud-based NHScompliant solution that ensures patient data security. Sites will pseudonymise scans prior to uploading to UEA servers. Access to the database, SIEP and brain imaging files will be via unique, individually assigned (i.e. not generic) usernames and passwords, and only accessible to members of the SIGHT trial team, and external regulators if requested. The servers are protected by firewalls and are patched and maintained according to best practice. The physical location of the servers is protected physically and environmentally in accordance with University of East Anglia's General Information Security Policy 3 (GISP3: Physical and environmental security).

The REDCap database [81-82] and associated code have been developed by NCTU Data Management, in conjunction with the SIGHT trial team. The database software provides a number of features to help maintain data quality, including; maintaining an audit trail, allowing custom validations on all data, allowing users to raise data query requests, and search facilities to identify validation failure/ missing data.

After completion of the trial the UK database will be retained on the servers of NCTU for a period of at least a year after publication of the primary outcome, for on-going secondary analyses, after which the CI or their delegate will initiate a request for the study database to be archived by NCTU. It will then be taken offline and archived as per NCTU_DM WI_4_Electronic Archiving. A copy will be provided to Sponsor for facilitating data requests.

The identification, screening and enrolment logs, linking participant identifiable data to the pseudonymised PID, will be held centrally by NCTU in a database or at site in written form in a locked filing cabinet or electronically in password protected form. After completion of the trial the identification, screening and enrolment logs will be stored securely for 10 years and then securely deleted.

5.10.3 Non-Adherence and Non-Retention

Reasons for non-adherence will be recorded where possible. Primary outcome data will be recorded for all those randomised.

5.10.4 Statistical Methods

5.10.4.1 Outcomes

Analysis will be conducted according to random group allocation (intention-to-treat principle). Baseline characteristics of the participants will be summarised using descriptive statistics by groups, n (%) for binary and categorical variables and mean (SD)/median (QIR) for continuous variables. Flow of the participants through the trial will be reported using the CONSORT flow diagram. A descriptive summary of the treatment received as well as adherence and fidelity measures will be given. A full statistical analysis plan will be pre-registered prior to completion of data collection, thus adhering to open and replicable research practices.

The clinical efficacy analysis will compare continuous outcome variables between treatment groups, using a general linear model at each time-point separately adjusting for stratification factors. To account for potential TAU variability across sites, clinical centre will be used as a co-variate. The effect of treatment will be summarised using the adjusted mean difference and 95% confidence interval. Dependent variables will include: Star Cancellation score (primary), CBS KF-NAP score, line bisection error and OCS Hearts overall, ego- and all centric scores and SIS scores in each domain.

The evaluation of mechanistic determinants of response to therapy will be modelled using a general linear model using the following baseline data: structural connectivity as per fractional anisotropy of fibres connecting IPS seed-regions and defined areas in the rest of the brain; inter-hemispheric (left-right) functional connectivity as per time course correlations between IPS seed-regions and rest of the brain; perception-grasping score computed from difference in deviation from rod centre between grasping and perception; stroke severity; visual field VISA sub-test score; and, OCS domain scores. To determine if treatment effect is modified by these mechanistic variables, we will correlate change scores (from baseline to T1, i.e. therapy response; Fig.2) and each of these measures while regressing out lesion volume (computed from the lesion map) as lesion size correlates with stroke recovery [28]. Each data will be included separately and then data reduction methods will be applied so that all the measures can be included in a single model. The study investigating IPS will test effects in each arm separately as well as test for an interaction to see if the association is different in the two arms. In addition, to determine if lesion location predicts treatment response (hypothesis 2), we will use lesion-symptom mapping analysis and test if specific lesion sites are associated with smaller change scores/therapy response.

If patients receive less than 70% of the intervention, they will be included in the intention-totreat efficacy analysis and T1 and T2 measures will still be collected and included in the mechanistic analysis to predict overall neglect recovery. An additional per-protocol analysis will be conducted in which these individuals will be excluded so that we can differentiate the effect of being allocated to the intervention (the intention-to-treat analysis) and the effect of the intervention if the participant, and therapist, adhere (the per-protocol analysis).

Site will be used as strata for the randomisation; this should remove any potential confounding for TAU variation across sites. In the analysis we will report the 'dose' given to the participants. We will carry out a per-protocol analysis including individuals who have received an appropriate dose of SIGHT (>70%). In the intervention group, we will correlate the amount of therapy received against the change in the primary outcome measure.

Missing data will be excluded in the primary analysis. However, the sensitivity of the missing data on the outcomes will be assessed by carrying out multiple imputation assuming that the data is missing at random. If we have reason to believe that the data is not missing at random, then pattern mixture models will be used to assess sensitivity.

Adverse events will be recorded including falls and classified in terms of seriousness and relatedness and a between group analysis will be conducted for those related to the study and overall to examine if therapy has an impact on number of falls.

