superior fronto-occipital fasciculus (SFO), is also relevant as it is significantly associated with severity of both egocentric and allocentric neglect [54]. In addition, resting-state functional magnetic resonance imaging (rsfMRI) studies in neglect have repeatedly shown that the connectivity of the structurally intact IPS to other brain regions within the damaged hemisphere seems key [28-30;58]. Specifically, interhemispheric (left-right) functional connectivity between the IPS and the rest of the brain is the most robust correlate of neglect deficits at 2 weeks post-stroke (r=0.55; p<0.001, N=25 neglect patients [28]). In fact, interhemispheric (left-right) functional connectivity between the IPS and the rest of the IPS and the rest of the brain even predicts neglect improvement at 12-weeks post-stroke (r=0.58; p<0.001, N=25 neglect patients [28]).

Thus, the mechanistic study embedded into the proposed efficacy trial aims to test if both behavioural and neuroimaging measures can be used as determinants of therapy response (Fig.2). Our testable hypothesis, based on the neuroimaging studies reviewed above, is that neglect patients with structural or functional damage to IPS and/or its projections will benefit less from SIGHT [16]. Notably, it is important to acknowledge, as highlighted above, that the neglect syndrome does not occur in isolation, but is often accompanied by other post-stroke visual and cognitive deficits (e.g., hemianopia and executive functioning) which also further impede stroke recovery and functional outcome [57]. Thus, to carefully examine the impact of these factors, our mechanistic study will combine innovative neuroscience and clinical expertise to characterize each patient's residual IPS structure and function, perception-grasping dissociation, cognitive and visual profile and stroke severity, and test if these measures can determine response to SIGHT, following MRC and American Society of Neurorehabilitation guidelines [31-33].

[figure not shown]

Figure 2. Mechanistic study of determinants of response to therapy.

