4.2 Objectives

This multicentre RCT aims to investigate the clinical efficacy of SIGHT on post-stroke neglect when delivered by a therapist in tightly controlled within-hospital settings, whilst simultaneously determining the causes of differing responses to therapy between individuals. Our primary research aims are to:

(1) determine whether SIGHT in addition to TAU produces greater reduction in neglect than TAU alone (i.e., standard occupational therapy for neglect).

(2) determine whether benefits from SIGHT are still evident at the 12-week follow-up after the intervention ends.

(3) determine if therapy response is modified by: (a) lesion location; (b) left and right IPS functional connectivity; (c) left and right IPS structural connectivity; (d) perception-grasping dissociation; (e) stroke severity, (f) visual and/or (g) cognitive deficits.

Our testable hypotheses, generated by our early phase work and neuroimaging studies [16,19-20,26-27], are that:

(1) when added to treatment as usual (TAU), 30 minutes/day of SIGHT for 7 days (over a 10-day period) will produce greater reduction in neglect than TAU alone.

(2) patients with impaired IPS structure or function will benefit less from SIGHT.

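### For five of the seven factors in objective 3, correlating change scores with baseline measures cannot separate a predictor of recovery from a modifier of the SIGHT effect

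*Protocol*

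**What the plan says.** Protocol section 4.2 lists effect modification among the primary research aims: "determine if therapy response is modified by: (a) lesion location; (b) left and right IPS functional connectivity; (c) left and right IPS structural connectivity", followed by (d) perception-grasping dissociation, (e) stroke severity, (f) visual deficits and (g) cognitive deficits. Hypothesis 2 is that "patients with impaired IPS structure or function will benefit less from SIGHT".

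Section 5.10.4.1 gives the method: "To determine if treatment effect is modified by these mechanistic variables, we will correlate change scores". The change is defined as "from baseline to T1, i.e. therapy response; Fig.2", so change and therapy response are treated as the same quantity. The only adjustment named for these correlations is "regressing out lesion volume (computed from the lesion map) as lesion size correlates with stroke recovery". Baseline Star Cancellation score and treatment arm are not named.

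One exception follows: "The study investigating IPS will test effects in each arm separately as well as test for an interaction". Lesion location is handled by lesion-symptom mapping, which will "test if specific lesion sites are associated with smaller change scores/therapy response". That analysis is tied to hypothesis 2, and no arm term is stated for it.

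Section 5.7 sizes the imaging study at 40 per group, including 20% attrition, for more than 90% power at the 2.5% level to detect r=0.58 within each arm separately. The same section says that some improvement will occur in both arms and that neglect severity strongly predicts recovery.

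**The concern.** A treatment effect is a contrast between arms, and a modifier is a factor across which that contrast differs. A patient's own change is natural recovery, plus measurement error, plus any SIGHT effect. A factor that predicts recovery equally well with and without SIGHT will correlate with change while modifying nothing. This is so whether the correlation is pooled or taken within the SIGHT arm. The protocol does not say which it will be for the non-IPS factors.

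There is a second route to the same error. Star Cancellation stops at 54, so patients who start high have little to gain. Any factor associated with baseline severity is then associated with change, and regressing out lesion volume does not reliably remove this.

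At stake is the purpose of the embedded study, which is to say who responds to SIGHT. General predictors of neglect recovery could be reported as determinants of SIGHT response and carried into patient selection for a later trial. The primary efficacy comparison is not affected.

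**Working it through.** **1. The plan's own figure.** Evaluable imaging patients per arm: 40 × 0.8 = 32. By Fisher's z, power = Φ(atanh(r)·√(n−3) − z). With r=0.58, n=32 and two-sided 2.5% (sidedness is not stated; z=2.241): atanh(0.58)=0.6625, 0.6625 × √29 = 3.567, Φ(1.326) = 90.8%. The stated power of over 90% is reproduced, for a correlation within one arm.

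**2. A purely prognostic factor.** Evaluable patients in the whole trial: 206 × 0.8 ≈ 164, or 82 per arm. The correlation r is an assumption, equal in both arms, so true modification is zero. At two-sided 5%:

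- r=0.2, n=164: 0.2027 × √161 = 2.572, Φ(2.572 − 1.960) = 73%
- r=0.3, n=164: 0.3095 × √161 = 3.927, Φ(1.967) = 97.5%
- r=0.2, n=82: 0.2027 × √79 = 1.802, Φ(−0.158) = 44%
- r=0.3, n=82: 0.3095 × √79 = 2.751, Φ(0.791) = 79%

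A simulation (4,000 replicates, 82 per arm, treatment main effect 0.51 SD, no interaction) agrees. For r=0.2 and 0.3 the pooled correlation is significant in 71% and 97% of trials, and the SIGHT-arm correlation in 45% and 80%. The arm-by-factor interaction is significant in about 5%.

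**3. A factor linked only to baseline severity.** All inputs are assumed: baseline normal with mean 36 and SD 12, truncated to 0–51; T1 = baseline + a fraction of the gap to 54 + noise with SD 6, held within 0–54; no SIGHT effect and no effect of the factor. There were 2,000 replicates at n=164.

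| Share of gap recovered | Factor–baseline r | Mean r with change | Correlation p<0.05 | Baseline-adjusted arm × factor p<0.05 |
|---|---|---|---|---|
| 15% | 0.30 | −0.08 | 17% | 5% |
| 15% | 0.55 | −0.15 | 49% | 5% |
| 35% | 0.30 | −0.16 | 57% | 5% |
| 35% | 0.55 | −0.30 | 98% | 5% |

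For scale, the poor recoverers described in section 5.7 went from a median of 26 to 35 between days 2 and 9, which is (35−26)/(54−26) = 32% of the gap. Participants enter later, from one week, so a smaller share is plausible.

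**4. Power of the interaction already planned for IPS.** Difference of two independent correlations at 32 per arm: SE = √(2/29) = 0.2626. Power = Φ((atanh(0.58) − atanh(r_TAU))/SE − 1.960). The TAU-arm r is not in the protocol and is assumed.

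| TAU-arm r | Power at 5% | Evaluable per arm for 90% power |
|---|---|---|
| 0 | 71% | 51 |
| 0.2 | 42% | 103 |
| 0.3 | 27% | 172 |
| 0.4 | 15% | 372 |

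**The case against.** **The plan already contains an interaction test.** This is true for IPS connectivity, and it stands. A reader might infer that all of objective 3 would be answered wrongly, but 3(b) and 3(c) have a valid test. In a check at 32 per arm, with a factor tied to baseline, that interaction on unadjusted change scores rejected about 4% of the time, so coupling with baseline does not bias it. For IPS only the within-arm correlations are open to misreading.

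**The most striking figures belong to the covered factor.** Both r=0.58 with later improvement and r=0.55 with neglect deficit (section 4.1) concern IPS connectivity. A reader might take 0.58 as a correlation in untreated patients, but the protocol says only that connectivity predicted improvement. A reader might also infer that coupling with baseline would reverse hypothesis 2. That sits badly with 0.58, which as printed links connectivity with more improvement, so no direction should be claimed. For the other five factors the protocol gives no correlation with baseline or with recovery.

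**The baseline-coupling rates depend on the scenario.** This also stands, and is why a range is given. The simulation leaves out the planned lesion-volume adjustment. If lesion volume correlated 0.5 with baseline severity (assumed), the top figure of 98% would fall to about 87%. It also truncates baseline at 51, whereas patients above 51 can enter through line bisection or the Oxford Cognitive Screen (section 5.3.1.2). The rates are for a single factor and do not carry over directly to lesion mapping across many sites; the reasoning does.

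**The statistical analysis plan could settle this.** Covariates can be left to it, and the protocol speaks of a general linear model. But the protocol itself names the change-score correlation as the test of whether the treatment effect is modified. That is a stated rule that needs correcting, not a detail left open.

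**Conclusion.** The point holds for lesion location (3a), perception-grasping dissociation (3d), stroke severity (3e), visual deficits (3f) and cognitive deficits (3g). As written, their analysis cannot tell a prognostic factor from a modifier of the SIGHT effect. This follows from the design and needs no assumed number.

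The size does rest on assumptions. With no modification, an equally prognostic factor is declared significant in about 73% to 98% of trials at n=164 (r=0.2 to 0.3), and in 79% at n=82 for r=0.3. A factor related only to baseline severity is falsely significant in about 17% to 98% at n=164, for 15–35% recovery of the gap and a factor–baseline correlation of 0.3–0.55. The arm-by-factor interaction stays near 5% in all these scenarios.

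For 3(b) and 3(c) the planned interaction is valid. What remains is that the sample was sized for a different quantity: 15% to 71% power for the interaction, against over 90% for the within-arm correlation.

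**What to change.** In section 5.10.4.1, for every factor in objective 3 including lesion location, define the test of modification as the arm × factor coefficient, with its 95% confidence interval, from one model across both arms:

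T1 Star Cancellation = arm + factor + arm × factor + baseline Star Cancellation + lesion volume + stratification factors.

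For lesion mapping, the corresponding term is lesion × arm. Keep the pooled and within-arm change-score correlations and the lesion maps if wanted, labelled as describing recovery rather than response to SIGHT.

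In section 5.7, say that the power of over 90% applies to correlations within each arm and not to effect modification, and give the interaction power at 32 evaluable per arm with the assumed TAU-arm correlation beside it.

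Optionally, pre-specify the IPS-preserved yes/no randomisation factor as a moderator. It is known for everyone randomised, but it is an added analysis and the correction does not depend on it.

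The cost: no extra patients or measurements. Interaction estimates have wider intervals, so fewer factors will reach significance. For IPS the correlations that the sample was sized for become descriptive, and the test that addresses modification is underpowered unless the two arms' correlations differ greatly. A null IPS interaction should therefore be reported with its interval and not read as absence of modification.

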5.4.1 Arm A – Standard care, treatment as usual

Participants allocated to Arm A will only receive TAU according to NICE guidelines [42] as provided routinely in their clinical centre. TAU will be recorded for each patient and at site level.

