5.4.2 Arm B – SIGHT Intervention + treatment as usual (TAU)

Participants allocated to Arm B will receive SIGHT for 7 days (30min/day) in addition to TAU over a 10-day period.

The staff delivering SIGHT will set-up the intervention in a separate room to reduce contamination (e.g., patients in Arm A being unblinded). The daily location of therapy delivery will be recorded in the CRF.

The SIGHT therapy involves repeated grasping and moving rods using the less affected arm. Three black lightweight wooden rods are used in different repetitions according to a pre-specified checklist. The therapist simply informs the participant about instructions following a pre-specified checklist and records the number of repetitions completed in each repetition and session.

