5.4.2.1 Dose Interruptions and Discontinuations

In cases where participants are unable to complete the 7 sessions within the 10-day window (e.g., due to illness), the intervention team can administer additional therapy sessions to replace the missed sessions. Efficacy measures will still be undertaken between day 11 and day 16 even if intervention delivery is delayed. Therapists delivering intervention will not communicate delays in intervention delivery to blinded assessors undertaking the outcome measures at T1 and T2.

Consistent with intention to treat analysis, patients who decline to continue the intervention (i.e. discontinuations) but who agree to completion of follow-up measures will remain in the trial.

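### The per-protocol analysis filters only the SIGHT arm by dose, so it is not a randomised estimate of the effect under adherence that the Protocol says it gives

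*Protocol*

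**What the plan says.** Section 5.10.4.1 makes intention-to-treat the main analysis and keeps under-dosed patients in it: "If patients receive less than 70% of the intervention, they will be included in the intention-totreat efficacy analysis". It then adds a second analysis: "An additional per-protocol analysis will be conducted in which these individuals will be excluded so that we can differentiate" two quantities, the effect of being allocated to SIGHT and "the effect of the intervention if the participant, and therapist, adhere (the per-protocol analysis").

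The next paragraph of the same section describes the per-protocol set again, by inclusion: "We will carry out a per-protocol analysis including individuals who have received an appropriate dose of SIGHT (>70"%). The paragraph ends with a planned correlation, within the intervention arm, between the amount of therapy and the change in the primary outcome.

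Three other places bear on this:

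- Comparator (5.4.1): "Participants allocated to Arm A will only receive TAU according to NICE guidelines". There is no sham and no SIGHT dose in this arm.
- Planned dose (5.4.2): "Participants allocated to Arm B will receive SIGHT for 7 days (30min/day) in addition to TAU over a 10-day period".
- Missed sessions (5.4.2.1): patients may be "unable to complete the 7 sessions within the 10-day window (e.g., due to illness"), and missed sessions may be replaced. The outcome visit does not move: "Efficacy measures will still be undertaken between day 11 and day 16 even if intervention delivery is delayed".

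**The concern.** A dose threshold for SIGHT can remove only patients who were allocated SIGHT. The same kind of patient in Arm A, who would have missed sessions if allocated to SIGHT, cannot be identified and stays in. After the exclusion the SIGHT group is selected on something that happened after randomisation and the TAU group is not. The difference between them mixes any treatment effect with the difference in prognosis between people who attend and people who do not.

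The Protocol does not present this as a rough supportive check. It states what the contrast estimates, namely the effect when the intervention is adhered to, and one-arm exclusion does not deliver that. The stated covariates (centre, age band, Star Cancellation band, IPS status) are fixed at baseline and do not capture illness or complications arising during the ten days of therapy.

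Two smaller points go with it. The two descriptions of the per-protocol set are not aligned. Nothing says whether replacement sessions given after the T1 assessment count towards 70% in the T1 analysis.

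**Working it through.** **The Protocol's own figures (5.7).** 0.51 × 12 = 6.12, the stated difference of about 6.1 points. A two-sample t-test with effect size 0.51, two-sided 5% and 90% power needs 82 per arm; 82/0.80 = 102.5, so 103 per arm and 206 in all. Both reproduce. The Protocol gives no figure for the per-protocol analysis.

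**Where the cut falls.** 0.70 × 7 = 4.9. If dose is counted in sessions, 5 or more is in and 4 or fewer is out, and nobody sits exactly at 70%. The mismatch between below 70% (out) and above 70% (in) would matter only if dose were counted in minutes or repetitions.

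**Bias in closed form.** Let q be the share of SIGHT patients excluded, A the mean T1 score adherers would have without treatment, and g how many points lower the excluded patients would score without treatment. By randomisation the TAU mean is

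M = (1 − q)·A + q·(A − g) = A − q·g.

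The per-protocol contrast is therefore (A + effect in adherers) − M = effect in adherers + q·g. The bias is q·g. It is zero if g = 0 and negative if the excluded patients are the better recoverers.

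**Inputs.** The Protocol states neither q nor g. Assumed: q from 10% to 25%; g, after covariate adjustment, from −6 to +12 points (−0.5 to +1 SD at SD 12).

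| q | g | bias (points) | share of 6.1 |
|---|---|---|---|
| 0.25 | −6 | −1.5 | −25% |
| 0.10 | −6 | −0.6 | −10% |
| any | 0 | 0 | 0 |
| 0.10 | +6 | +0.6 | +10% |
| 0.20 | +6 | +1.2 | +20% |
| 0.25 | +12 | +3.0 | +49% |

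**Why both signs are possible.** Sections 5.4.2.1 and 5.11.2 name illness and stroke complications as reasons for disrupted delivery, which gives g > 0. But SIGHT is given in hospital (5.1.1), and the discharge exclusion looks 7 days ahead (5.3.1.3) against a 10-day therapy period, so a patient who recovers quickly and goes home can also miss sessions, which gives g < 0.

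**Simulation check.** No true effect, 82 per arm, SD 12, baseline-adjusted linear model, 3,000 runs, 20% excluded. Attendance is driven by an unmeasured factor with correlation r to the residual outcome. The baseline–outcome correlation of 0.6 and the values of r are assumptions.

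| r | per-protocol bias | type I error |
|---|---|---|
| −0.3 | −1.00 | 9.0% |
| 0 | +0.01 | 4.2% |
| +0.3 | +1.04 | 9.1% |
| +0.5 | +1.61 | 17.4% |

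Across all scenarios run (10%, 20% and 30% excluded) the intention-to-treat estimate stayed between −0.07 and +0.05 points.

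**What the alternative recovers.** Suppose 20% are under-dosed and gain nothing, and adherers gain 6.1. Intention-to-treat gives 0.8 × 6.1 = 4.9. The complier-average estimate is 4.88/0.8 = 6.1. The planned contrast with g = 6 gives 6.1 + 0.2 × 6 = 7.3.

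**Where the alternative can fail.** If the under-dosed 20% gain half, intention-to-treat gives 0.8 × 6.1 + 0.2 × 3.05 = 5.49, and dividing by 0.8 gives 6.86, which is 0.76 too high. If they gained half because they received half the sessions, mean dose is 0.8 + 0.2 × 0.5 = 0.9 of the full course and 5.49/0.9 = 6.1. This is why sessions completed is the better main exposure and the 70% split the secondary one.

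**The case against.** The strongest reply is that this is a conventional supplementary analysis. Intention-to-treat is the main analysis, the per-protocol analysis is called additional, dose and fidelity are reported alongside, and a full statistical analysis plan is promised. Exact set definitions and session counting usually belong there. All of that stands, and it limits the weight of the point. It does not remove it, because the Protocol already fixes both the exclusion and its causal meaning.

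A reader might infer that the analysis is biased towards SIGHT. The documents do not establish the direction: the named reasons make it more likely, but the hospital-only setting leaves room for the opposite.

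The size is also assumption times assumption. The closest data, in section 4.1, are 6 of 6 patients completing the computerised version at home. That is reassuring but small: the one-sided 95% upper limit for non-completion is 1 − 0.05^(1/6) = 39%. The green criterion in 5.12.2, a median of at least 75% of sessions, still allows just under half the arm below 70%. Adjustment for baseline severity, and the exclusion of missing outcomes in both arms, may shrink the gap, so a full 1 SD is an extreme case.

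Read in isolation, the second definition would leave no TAU patients, since none receives SIGHT. Taken with the preceding paragraph the intent is clear, so this calls for aligned wording only. Likewise, section 5.4.2.1 does not say that sessions after T1 count as treatment for T1; the rule is simply not fixed. The within-arm dose correlation involves no comparison between arms and carries no causal claim. It may be confounded by prognosis, which is a separate weakness.

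Finally, nothing ties the per-protocol result to the phase III design; section 5.5.2.1 makes that link for the Stroke Impact Scale only.

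**Conclusion.** The point holds as a wrong claim about what an analysis estimates. Excluding under-dosed SIGHT patients with no possible counterpart in TAU gives a non-randomised contrast, and the Protocol labels it the effect under adherence. The likely direction is towards SIGHT, but it could be against, or nil. The illustrative size, −1.5 to +3.0 points or about −25% to +49% of the target difference, rests wholly on the assumed share and gap and is not a forecast. It would be wrong to infer that the primary conclusion is at risk: the intention-to-treat analysis keeps the randomised comparison. This is a correction that should be made, not one on which the trial's main result depends.

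**What to change.** - Estimate the effect under adherence with a complier-average analysis: two-stage least squares, randomised allocation as instrument, the primary model's covariates, and number of sessions completed as the main exposure. State that allocation is assumed to act only through sessions received, and that reading the result as the effect of a full course assumes benefit roughly proportional to sessions.
- Report the 70% split as a secondary version, with its assumption of no benefit below 70% stated.
- Check for any SIGHT exposure in TAU before treating non-adherence as one-sided, since sections 4.3, 5.1.2.4 and 5.9.2 treat contamination as a risk.
- If the per-protocol contrast is kept, label it non-randomised and supportive, and withdraw the statement that it gives the effect under adherence.
- Align the two definitions in 5.10.4.1, and say whether 70% counts sessions, minutes or repetitions.
- Count only sessions delivered before the T1 assessment as exposure in the T1 analysis, and all sessions before T2 in the T2 analysis.
- Label the within-arm correlation of dose with change as descriptive.

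The cost is mainly wording. The Protocol says that location and repetitions are recorded, but does not say outright that session dates are, so the case report form should be checked for them. The statistical cost is a wider interval: with 80% adhering, the version using the 70% split is about 1/0.8 = 1.25 times as wide as the intention-to-treat interval. The assumptions above cannot be fully tested.
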